6.2.2 Enrollment, Baseline, and/or Randomization

Enrollment

Identification of families (i.e., households): We will group families using one of two possible methods. First, LACDHS has an identifier that ties family members together. It is called the "Family Budget Unit." We will explore this method. If it does not work, we will use another method that we have utilized successfully in the UCLA-based study from which this study is derived. We will assume that people living in the same address belong to the same family. As a secondary measure, we use a

telephone number as a linking number (i.e., if two people have the same telephone number, we assume they are from the same household).

Baseline Assessments

Vaccination status. We will assess baseline vaccination status at the beginning of the flu season as we will exclude individuals who have already received their vaccination.

Randomization

We will randomly allocate families to one of the study arms shown above and send family members the allocated text message. All family members will therefore receive the same text message. This is meant to reduce confusion among patients. For the analysis, we will randomly select one index patient per household for analysis. This follows Cochrane criteria for being included in meta-analyses. We will attempt to affiliate index patients with practices, and randomize patients (families) within these practices.

The retrospective analysis will result in a randomization and personalization template that will include placeholders and calculations for the following items: a) patient contact information, b) experimental group assignment, c) message contact dates (one per month in batches of 100 patients per day), d) randomly assigned message contact channel for each contact date (e.g. phone, portal, email, SMS), e) message templates with substitutable text, f) personalized message content for each month of messages, and g) stratification and personalization data elements identified in the retrospective analysis. These templates will be populated on premises at LACDHS with data to be retrieved by the Informatics Core staff. These randomized lists will be converted to personalized, tailored messages based on Mail Merge templates or similar DHS campaign management software. After lists and personalization have been completed, they will be approved by the research team in a final cross-check. All patients that have been vaccinated will be removed from contact lists before each wave of messages is delivered. These templated assignments may be moved from Excel to DHS Reporting Software (ELM) or other campaign management software by the Informatics Core.

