4.2 Exclusion Criteria

The exclusion criterion is a patient age of < 6 months, as babies less than 6 months are not eligible for influenza vaccination. We will also exclude individuals who have already received their flu vaccination this season.

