5. STUDY INTERVENTIONS

5.1 Interventions, Administration, and Duration

Text messages will begin to be sent at the beginning of the 2022 flu season. We will randomly spread out the calls throughout the day and week in order to minimize unnecessary overload for the call center when patients text back a “1” response that they would like a

call or text message to help them. We can do this by randomizing patients into batches so that there is no systematic time-of-day or day-of-week for any patients. We will send up to 3 reminders this flu season.

Control arm: Standard Texts (n=232,950). Patient randomized to this study arm will receive up to 3 text messages, reminding them about the importance of influenza vaccination. The messages themselves are shown below. The standard texts will include a clinic call back number and patient portal self-scheduling for patients to schedule their influenza vaccines. The direct scheduling texts includes a direct number to an agent that can help schedule and answer questions on the phone in real time. The texts with a direct number to schedule will link a specified phone number to call and schedule. This number would be answered by a central agent quickly and a patient could schedule their flu shot at any clinic site. This specific phone number would not go through the multiple option menus a patient would normally experience when calling their clinic.

Intervention arm: Standard Texts with Transportation (n=3,050). The standard texts with transportation includes phone number for patients to reserve transportation to a vaccination appointment based on Medi-Cal health plan transportation resources.

Prepped Text Messages for DHS Flu Campaign 2022 - 2023

Standard Text:

#PCM#H: #FirstName#, your flu shot is ready! Call your clinic at #ExternalRefNo# or visit the LA Health Portal at <http://bit.ly/BookFluShot> if you want this shot held for you.

Standard Texts (+ Transportation)

#PCM#H: #FirstName#, your flu shot is ready! Call your clinic at #ExternalRefNo# or visit the LA Health Portal at <http://bit.ly/BookFluShot> if you want this shot held for you. You can call #Health Plan Phone Number# to schedule a free ride your flu shot through #Health Plan Name#

Examples (Transportation)

- Standard Texts (+ Transportation) - LA Care**

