5.2 Handling of Study Interventions

As we will send up to 3 text messages during the flu season, we will search the EHR for whether or not the patient received an influenza vaccination this season. If yes, the patients will be dropped from the denominator of patients needing a text message reminder. We will search the EHR prior to each of the text message rounds. Review of medical records is needed in order to obtain the information about (a) influenza vaccination dates this upcoming season, and (b) address (in order to group patients into households as described above. We will review the EHR prior to each round of text messages to see if patients had received an influenza this season.

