9.5 Data Analyses

Statistical Analysis Plan

We will perform separate evaluations of the impact of the text enhancements (callback and bidirectional texting) on the one hand, and transportation messaging on the other hand. Primary outcomes will be evaluated as a test of differences between proportions vaccinated in control and treatment groups, and heterogeneity of treatment effects will separately analyze subgroups. For further analyses, we will use multivariable log-binomial regression models with vaccination status at the end of the campaign as the outcome variable. Regressions will include indicators for each intervention as fixed effects, with the standard text condition as the reference group, and potentially clinic random effects, depending on retrospective analysis results. Models will also adjust for patient age, gender, race/ethnicity, insurance, and whether the patient was vaccinated in at least one of the prior two flu seasons. Secondary analysis will include subgroup interactions with intervention indicators to assess heterogeneity of treatment effects. In exploratory analyses, we will investigate interactions between interventions, questions related to modality of message delivery, as well as whether encounter type, click rates on messages, and distance to the health care facility from the home address affect influenza vaccination rates.

In addition, we will evaluate the loss to follow-through rates (scheduling an appointment, but did not complete the appointment) by patient demographics, as distance to the health care facility from the home address).

For the evaluation of text enhancements, we will perform a 3-fold Bonferroni correction accounting for pairwise comparison of intervention arms, using a two-sided significance level of 0.017. For the evaluation of transportation messaging, we will use a two-sided significance level of 0.05. All analyses will be intention-to-treat, and will be performed using SAS v. 9.4 (SAS Institute Inc., Cary, NC).

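### Patients vaccinated after randomization but before their scheduled first text stay in the intention-to-treat comparison, which slightly dilutes the effect and costs some power without biasing it

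*Combined protocol and SAP*

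**What the plan says.** - Eligibility: section 4.2 says "We will also exclude individuals who have already received their flu vaccination this season", with no cut-off date. Section 6.2.2 puts it into operation: "We will assess baseline vaccination status at the beginning of the flu season as we will exclude individuals who have already received their vaccination".
- Timing of texts: section 5.1 says "Text messages will begin to be sent at the beginning of the 2022 flu season" and spreads contacts at random: "We can do this by randomizing patients into batches so that there is no systematic time-of-day or day-of-week for any patients". The randomization template in 6.2.2 lists "message contact dates (one per month in batches of 100 patients per day" among its items.
- Later checks: section 5.2 says "We will search the EHR prior to each of the text message rounds", and vaccinated patients then no longer count among those due a reminder. Section 6.2.2 adds: "All patients that have been vaccinated will be removed from contact lists before each wave of messages is delivered". Neither sentence mentions the analysis set.
- Schedule of evaluations (6.1): vaccination status is marked at screening, at Day 1 (enrollment and randomization) and at intervention start (Month 1). The table does not say whether the later marks affect eligibility.
- Analysis: section 9.5 says "All analyses will be intention-to-treat". The primary outcome (9.4.1) is end-of-season status in the state registry.

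**The concern.** Read together, these sections leave a gap between the point at which the exclusion is applied and the point at which a household can first be influenced. Someone randomized and then vaccinated inside that gap either leaves the contact list unsent or is texted when the text can no longer change anything. In both cases intention-to-treat keeps that person as a success in the assigned arm.

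Such patients add the same vaccinated share to each arm. They carry no information about the intervention and pull the observed difference towards zero. The transportation arm, with 3,050 patients against 232,950 controls, has little power to spare. The plan also never defines time zero for a household, so an analyst has no written rule for these patients.

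**Working it through.** **1. The plan's own figure.** Section 9.2 states 80% power for a 2% impact. Inputs: n = 232,950 and 3,050 (5.1), two-sided 0.05 (9.5), and a control rate of 31.2% (2.1; a background figure, not stated as a power input). With 31.2% vs 33.2%, a pooled-variance two-proportion test gives 65.6%. The unpooled version used below gives SE = √(0.312×0.688/232,950 + 0.332×0.668/3,050) = 0.00858, z = 0.02/0.00858 = 2.33, power Φ(2.33 − 1.96) = 64.5%. The 80% is not reproduced. That is a separate matter; here about 65% is the baseline from which any dilution is subtracted.

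**2. The rollout window.** The template's 100 patients per day cannot be the overall rate: 236,000/100 = 2,360 days, against a 6-month period. Applied to the transportation arm alone (an assumption) it gives 3,050/100 = 30.5, about 31 days. The spreading over the day and week in 5.1 suggests a window nearer 7 days. I therefore take 7 to 31 days.

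**3. The share q.** Assumption: uptake accrues evenly to 31.2% over 182 days and first texts are spread evenly over a window of w days, so the mean wait is w/2 and q = 0.312 × (w/2)/182. A second line doubles the early uptake rate.

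| Window | q, even uptake | q, twice that rate |
|---|---|---|
| 7 days | 0.6% | 1.2% |
| 14 days | 1.2% | 2.4% |
| 31 days | 2.7% | 5.3% |

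**4. Effect and power.** Assume a 2-point effect among patients unvaccinated at their scheduled first text, and treat the arm sizes in 5.1 as analysed numbers.

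- Day 1 cohort: control rate 0.312, difference 0.02 × (1 − q), full n.
- First-text cohort: control rate (0.312 − q)/(1 − q), difference 0.02, both n multiplied by (1 − q).

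| q | Difference, Day 1 cohort | Power, Day 1 cohort | Power, first-text cohort | Gap |
|---|---|---|---|---|
| 0.6% | 1.99 points | 63.9% | 64.5% | 0.5 |
| 2% | 1.96 points | 62.7% | 64.6% | 1.8 |
| 5% | 1.90 points | 60.1% | 65.0% | 4.9 |

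Gaps are taken before rounding. Worked line for q = 5%: the Day 1 difference is 0.02 × 0.95 = 0.019. The first-text control rate is (0.312 − 0.05)/0.95 = 0.2758, with about 2,898 transportation patients. The smaller cohort has the higher power because it removes patients who contribute only dilution. Pooled variance gives similar gaps: 63.9% vs 65.8% at 2%, and 61.2% vs 66.4% at 5%.

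**5. Bias.** Batches are assigned at random and no text has reached the household before its scheduled date, so q has the same expectation in every arm. The difference is attenuated, but the arms remain comparable and type I error is not inflated.

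**The case against.** **No delay is stated.** The baseline check and the start of texting share one anchor, the beginning of the season. The Month 1 column in 6.1 pairs with Month 6 as the end of a 6-month period, so it can contain Day 1. A reader might infer a month's lag between randomization and first text; the documents do not support that. What stands is that batching creates some gap, of unstated length.

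**A single check is not stated either.** A reader might conclude that the exclusion is applied only once. Status is also marked at Day 1 and Month 1, and the EHR is searched before each round. No section, however, ties those checks to eligibility or to the analysis set, so the documents are silent rather than committed.

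**The planned check may not be fine enough.** Section 5.2 speaks of rounds and 6.2.2 of waves, a term it does not define. If the check is run once per round, a patient vaccinated between it and a later batch would still be texted. The dilution remains, but removing it may need a check per batch. This stands, and it is a cost of the fix.

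**The target may be the campaign effect.** A full intention-to-treat contrast from one allocation validly estimates what running the campaign achieves. If the 2% in 9.2 means that effect, nothing is lost against the stated target. This too stands: the loss described here is relative to a contrast among people the texts could still influence.

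**Households.** Section 5.1 batches patients, not families, so a relative could be texted before the index patient's own date. Any time-zero rule must therefore work at household level.

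**Conclusion.** The point holds as a modest loss of precision and a missing definition of time zero. For a first round of 7 to 31 days, q is about 0.6% to 5%, the 2-point effect shows as about 1.99 to 1.90 points, and about 0.5 to 5 points of power are given up in the transportation comparison. This rests on four assumptions: the uptake pattern, the window, a 31.2% control rate, and a 2-point effect placed among those unvaccinated at first text.

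Two stronger readings are not supported. One is that the comparison is biased; it is not, because the gap is unrelated to arm. The other is a large loss, such as a 10% share costing about 11 points of power (55.6% vs 66.6%); nothing in the documents points to a gap long enough for that. For windows up to about a month, the shortfall from the stated 80% at a 31.2% control rate is larger than this dilution. The change is still worth making, because it is cheap and the loss falls on a comparison with little power in reserve.

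**What to change.** In sections 4.2 and 6.2.2, set time zero at each household's scheduled first-text date and place all members of a household in the same batch.

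- **Preferred:** check vaccination status just before that date, then allocate the batch's households to arms, within practice as planned and with the same arm ratio in every batch. Draw the index patient from members still unvaccinated. Everyone randomized is then unvaccinated in the records at time zero, and strict intention-to-treat is kept.
- **If allocation is made once on Day 1:** define the primary analysis set by excluding patients whose recorded vaccination date precedes the scheduled first-text date. Apply the rule identically in every arm and blind to arm, and report the full Day 1 set as a sensitivity analysis. Use the scheduled date, not the actual sending, since selecting on what was sent after randomization could break comparability.

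State in 9.5 that later checks govern contact only and remove no one from the analysis.

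Cost: a slightly smaller analysed number (at q = 5%, about 2,898 instead of 3,050 in the transportation arm), allocation by batch in place of one list or else one extra analysis-set rule, household-level batching, and possibly a vaccination check per batch rather than per round.

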7. SAFETY ASSESSMENTS

7.1 Specification of Safety Parameters

There are minimal risks to participants in this study. None of the intervention strategies place patients at any additional risk of adverse outcomes, above and beyond the risks associated with routine immunization. Influenza vaccine is recommended by Advisory Committee on Immunization Practices (ACIP) for the patient population included in this study and administration of these vaccinations is part of the routine practice of immunization delivery.

Risks of immunization: Although rare, there are inherent risks to immunization with any vaccine. While the practice-based immunization efforts may increase the likelihood that patients will receive recommended vaccines, the study does not increase the risk (per vaccine) of a vaccine-related adverse event for any individual patient.

Risk of breach of confidentiality: In this study, an additional risk to subjects is the risk of a breach of confidentiality. A number of policies, procedures, and technical safeguards will be in place to ensure that there is no breach of confidentiality as a consequence of this study. These steps are outlined below in the “Protected Health Information” section. The study proposed is a minimal risk study, with a loss of confidentiality posing the greatest risk to the individual patients and participating practices, as data will be extracted from the EHR data of participating practices to provide study data for the research team. All study data will be prepared by the DHS-CTSI Informatics Core in accordance with the DHS Research Oversight Board policy. Only Limited Data Sets will be transferred for analysis purposes; compliance with the transfer process will be managed by Drs. [name] and [name] as DHS Co Investigator. Any links between identified data and deidentified data will be stored only on DHS premises. Patient contact lists and personalized data elements will be exclusively maintained on premises by the Informatics Core, responsible for implementing the patient assignment and personalization templates. Research data will be entered into a password-protected computer and will never be transferred to laptops or portable media.

Vaccination rates as compared to the control group. Although unlikely, it is possible that the interventions have the effect of reducing vaccine uptake; therefore, we will monitor vaccination rates in the intervention groups as compared to control group.

7.2 Methods and Timing for Assessing, Recording, and Analyzing Safety Parameters

Reports of our safety measures will be delivered to our Data Safety Monitoring Board at the cadence determined by the DSMB members (likely at 6 and 12 months post implementation).

7.3 Adverse Events

Potential adverse events include risks of side effects inherent to immunization with any vaccine. However, while the practice-based immunization efforts may increase the likelihood that patients will receive recommended vaccines, the study does not increase the risk (per vaccine) of a vaccine-related adverse event for any individual patient. Likewise, influenza vaccinations are universally recommended for all individuals greater than 6 months of age and is the standard of care. It is also possible that the interventions have the unlikely effect of reducing vaccine uptake. We will monitor vaccination rates as compared to the control group as a safety metric.

7.4 Reporting Procedures

The Principal Investigator will report any unanticipated events to the IRB as well as the Data Safety and Monitoring Board (DSMB) assembled for this study. When notified of an unanticipated event, the DSMB will convene and make a decision as to whether the study should continue. The IRB will also be notified of the DSMB's decision. *Please see detailed Data and Safety Monitoring Plan.*

7.5 Safety Monitoring

[name] as the study Principal Investigator will be responsible for monitoring participant safety, data quality/confidentiality, and evaluating the progress of the study on a daily basis in conjunction with study staff. Oversight for this study will be conducted by the Roybal Standing Data and Safety Monitoring Board. DSMB Membership will be reviewed and approved by the NIH. Should there be any questions regarding the independence of DSMB member(s), it will be addressed and corrected, if necessary, at that time.

The DSMB will have the role/responsibility of reviewing the entire IRB-approved study protocol regarding subject safety and analysis, and participant recruitment and retention milestones. At the time of interim analysis (50% enrollment), the study team will prepare a safety report to be reviewed by the DSMB who will provide recommendations to the NIH for or against the trial's continuation, as well as any modification to the study.

8.

INTERVENTION DISCONTINUATION

Following each DSMB meeting/report, the board will make recommendations to the IRB as to whether the study should continue or if changes to the protocol are necessary for continuation.

9. STATISTICAL CONSIDERATIONS

9.1 General Design Issues

Design

Randomized controlled trial

Outcome Measures

Our primary outcome is the end of season influenza vaccination status based on California's statewide vaccine registry (CAIR2). Secondary outcomes include vaccination intentions as measured by patients' contact with appointment systems, scheduled vaccination appointments (and missed appointments), and influenza hospitalizations among patients that are eligible to receive vaccinations.

9.2 Sample Size

Our power calculation suggests that we have 80% power to detect a 2% impact of each intervention.

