2.1 Background on Condition, Disease, or Other Primary Study Focus

Compliance with influenza and COVID-19 vaccinations is a critical public health issue, and underserved populations are vulnerable to community spread and frequently have more adverse outcomes. “Mega-studies” of insured populations with a history of vaccination may not be representative of heterogeneous groups of uninsured and underinsured patients. Reasons for noncompliance are multifactorial: well-meaning policies related to increasing vaccine accessibility may not be widely understood or disseminated, employer-based incentives and mandates may not be applicable, and issues related to communication, trust, and safety remain challenges and vary among different communities. This study will be the first large-scale randomized controlled trial testing personalized behavioral interventions in an underserved population. The Los Angeles County Department of Health Services (LACDHS) eligible population is as large as prior “Mega-studies”, though substantially less adherent to vaccination (currently 31.2% at LACDHS vs. 42% in Milkman et al.,) with a comparatively large proportion of Hispanic and Black patients.

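### The 80% power for a 2% impact stated in section 9.2 does not reproduce for the transportation arm; the documents' own figures give about 66%

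*Combined protocol and SAP*

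**What the plan says.** Section 9.2 is a single sentence: "Our power calculation suggests that we have 80% power to detect a 2% impact of each intervention". It does not show how the figure was obtained.

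The ingredients of a power calculation for the transportation comparison appear elsewhere:

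- Arm sizes, section 5.1: "Intervention arm: Standard Texts with Transportation (n=3,050") and "Control arm: Standard Texts (n=232,950").
- Significance level, section 9.5: "For the evaluation of transportation messaging, we will use a two-sided significance level of 0.05". The same section makes the primary analysis a comparison of the proportions vaccinated and keeps regression for further analyses.
- Vaccination rate, section 2.1: the LACDHS population is described as "substantially less adherent to vaccination (currently 31.2% at LACDHS vs. 42% in" a published study of a different population. No other LACDHS rate is given.
- Exclusion, section 4.2: "We will also exclude individuals who have already received their flu vaccination this season". Section 6.2.2 gives the timing: "We will assess baseline vaccination status at the beginning of the flu season as we will exclude individuals who have already received their vaccination".
- Analysis unit, section 6.2.2: "For the analysis, we will randomly select one index patient per household for analysis".

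**The concern.** The claim in 9.2 covers each intervention, so it includes transportation, the pilot arm that this protocol describes. It is the only power statement for that comparison. The control arm is about 76 times as large as the transportation arm (232,950 / 3,050), so precision depends almost entirely on the 3,050. That number looks small for a 2-point difference when about a third of patients are vaccinated.

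What is at stake is how a null result will be read. Against 9.2, a non-significant transportation result would count as fairly good evidence against a 2-point effect, with a 20% chance of having missed it. If the control rate is near 31.2%, that chance is about 34%.

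**Working it through.** **Inputs.** n0 = 232,950 and n1 = 3,050 (5.1); two-sided alpha 0.05, so z = 1.960 (9.5); p0 = 0.312 (2.1, background figure); difference d = 0.02, reading 2% as percentage points, so p1 = 0.332.

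**Formula.** Two-proportion z-test, with pooled standard error under the null (SE0) and unpooled under the alternative (SE1):

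power = Φ[(d − z·SE0) / SE1]

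**The 9.2 claim with these inputs.**

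- Pooled proportion = (232,950 × 0.312 + 3,050 × 0.332) / 236,000 = 0.31226
- SE0 = √[0.31226 × 0.68774 × (1/232,950 + 1/3,050)] = 0.008446
- SE1 = √[0.312 × 0.688/232,950 + 0.332 × 0.668/3,050] = 0.008581
- (0.02 − 1.960 × 0.008446) / 0.008581 = 0.402, and Φ(0.402) = **65.6%**

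The stated 80% is not reproduced. Solving the same formula for d at 80% power gives **2.38 points**.

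**Other methods, same inputs.** Unpooled variance 64.5%; arcsine 65.1%; continuity correction 64.9%; a 2-point decrease 66.2%. A one-sided 0.05 test, contrary to 9.5, gives 76.2%. Reading 2% as relative (0.02 × 31.2 = 0.62 points) gives 11% to 12%. None reaches 80%.

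**Lower control rate after excluding the already vaccinated.** With all 3,050 analysed:

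| Control rate | Power for 2 points |
|---|---|
| 31.2% | 66% |
| 25% | 71% |
| 20% | 78% |
| 18.3% | 80% |

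Suppose 31.2% is the full-season rate (assumption) and a fraction f of the cohort is excluded before randomisation. The residual rate is (0.312 − f)/(1 − f). Assumed f of 2% / 5% / 10% gives residual rates of 29.8% / 27.6% / 23.6% and power of 67% / 69% / 73%. A residual rate of 18.3% needs f = (0.312 − 0.1833)/(1 − 0.1833) = 0.158. That is 0.158/0.312, or about half of everyone vaccinated that season, already vaccinated at a baseline that 6.2.2 places at the start of the season. The record checks before each message round (5.2) come after randomisation and only stop further messages. Under the intention-to-treat analysis in 9.5 they do not change the control rate.

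**Pooling transportation cells.** With p0 = 0.312 and n0 fixed, 80% power needs n1 of about 4,335. That implies a further transportation cell of about 4,335 − 3,050 = 1,285, which section 5.1 does not list.

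**One index patient per household.** Household size is not given. If 3,050 counts patients before index selection, dividing both arms by an assumed number of eligible members gives, at 31.2%:

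| Assumed members | Transportation patients analysed | Power for 2 points | Detectable at 80% (points) |
|---|---|---|---|
| 1.1 | 2,773 | 62% | 2.5 |
| 1.25 | 2,440 | 56% | 2.7 |
| 1.5 | 2,033 | 49% | 2.9 |
| 2 | 1,525 | 39% | 3.4 |

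If 3,050 already counts index patients, none of this loss applies.

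**The case against.** The strongest objection is that the control rate is imported. Section 9.2 states none, and 31.2% describes the LACDHS population in the background section, whereas the trial randomises only patients not yet vaccinated. At about 18% to 20% the stated power would be right or nearly so. This stands as a limit: the check shows that 80% does not follow from the figures given, not that an unseen calculation was wrong.

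A second objection is that 5.1 does not account for everyone. Section 4.1 gives over 273,000 eligible patients and the two arms total 236,000, leaving about 37,000. If all of these were excluded as already vaccinated (assumption), f = 37,000/273,000 = 13.6%, the residual rate is 20.4% and power is about 77%. That is still short of 80%, and it leaves nobody for the callback and bidirectional texting arms named in the Précis.

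Third, the Précis calls the design a 2 x 2 factorial, the design figure is not visible in the text reviewed, and 5.1 is not a complete list of cells. The regression in 9.5, with one indicator per intervention, would pool any transportation cells. A second cell of 3,050 (assumption) would give about 91% at 31.2%. This possibility remains open. However, the visible text gives only one transportation cell, the Précis compares every intervention with standard texts, and the primary test in 9.5 is a simple comparison of proportions.

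Finally, the household figures rest on assumed sizes and only show direction. It is also fair that this is a pilot arm and that the remedy is wording. Even so, the sentence is the only power claim for the protocol's own comparison.

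**Conclusion.** The concern holds. With 31.2% in control, 3,050 versus 232,950 analysed and a two-sided 0.05 test, power for 2 percentage points is about 66% rather than 80%, and the effect detectable with 80% power is about 2.4 points. This rests on 31.2% approximating the rate among randomised controls, on all 3,050 being analysed, and on no pooling. A lower control rate or pooled cells could raise power and household selection could lower it, but 9.2 addresses none of these. The conclusion is limited to the transportation arm; the sizes of the text-enhancement arms are not given, so their power cannot be checked.

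**What to change.** Rewrite 9.2 for the transportation comparison and state:

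- the control rate expected among those randomised, after the already vaccinated are excluded;
- the effect in percentage points;
- two-sided alpha 0.05;
- the number of index patients analysed in each arm;
- whether transportation cells are pooled under the factorial design and, if so, their sizes.

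If 31.2% is the intended control rate, wording could be: with 3,050 and 232,950 index patients analysed and 31.2% vaccinated in control, the trial has 80% power for about 2.4 percentage points and about 66% for 2 points; power is lower if fewer index patients are analysed. If a lower rate or pooled cells underlie the 80%, state that rate or those cell sizes instead.

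The cost is wording in 9.2. Enrolment, arms, allocation and analysis do not change.
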